# 6.5.1 Prohibited treatments during the study

Concomitant medication(s) that could affect the outcome of the study, interfere with the evaluation of the results or constitute a health risk for the study subject, as judged by

the investigator. These include e.g. vasoactive supporting medication(s) that have known effects on cardiac efficiency.

### 6.5.2 Permitted treatments during the study

Optimal standard HF therapy and other concomitant medication(s) needed for treatment of possible concurrent diseases are allowed.

### 6.6 Emergencies and treatment of adverse events

Emergencies will be treated according to the decision of the physician in charge or the investigator when available. The treatment of possible AEs will be primarily symptomatic.

Any relevant control or follow-up examinations may be initiated at any time by the investigator. In case of any clinically significant abnormalities, medical assistance is assured until complete resolution or stabilization.

### 6.7 Procedures for monitoring subject compliance

During the screening/run-in period, the subjects will take one tablet of valsartan twice a day at home. During the treatment period, the subjects will take one tablet of active drug and one placebo tablet twice a day at home. They will be instructed to take valsartan (during the run-in) and the study drugs (active and placebo) in the morning and in the evening. In case a subject forgets to take the tablet(s) in the morning or in the evening, he/she is instructed to take the next one at the next scheduled drug intake time. At each administration time during the treatment period, the subjects are instructed to take one tablet from each of the two study drug packages they were provided with at a previous site visit. Two study drug packages (one containing the active drug and one containing the placebo) will be dispensed to the subjects at the baseline visit and at visit 1 by an unblinded member of the study team. In case the dose of the study drug is down-titrated during the treatment period, new study drug packages may be dispensed after visit 1. The subjects will be asked to return the study drug packages at each site visit, with all of the unused tablets, both during the screening/run-in and treatment period. Study personnel will do a valsartan and study drug/placebo accountability check and record this when applicable (i.e. at baseline visit and visits 1 and 3; also at screening visit 2 and visit 2, if they are performed as site visits). Valsartan accountability check during the screening/run-in period may be performed by any member of the study team, whereas study drug/placebo accountability check during the treatment period has to be performed by the unblinded member of the study team.

Drug accountability records will be kept. The investigator or his/her delegate must maintain accurate written records demonstrating the date and amount of study drugs received at the site, to whom and by whom dispensed (drug dispensing list) and accounts of drugs accidentally or deliberately destroyed. Unused study drugs will be recorded and returned to the sponsor or disposed of, on the sponsor's consent. Any discrepancies between the returned and expected returned study drugs should be explained.

### 7 VISIT SCHEDULE

### 7.1 Screening/run-in period

The screening/run-in period can last up to 6 weeks, but is not intended to last over 4 weeks, before the first study drug administration in the double-blinded treatment period. In certain cases, if clinically indicated (e.g. tolerability issues) or necessary for other reasons (e.g. scheduling), the screening/run-in period may last longer than 6 weeks. Screening/run-in period extensions (over 6 weeks) must be justified by the investigator and the reasons documented. Screening/run-in safety assessments should be repeated, based on investigator's judgement and/or if necessary, so that the laboratory results and the latest BP values are no older than 6 weeks.

During the first screening visit, a potential study subject will receive both written and verbal information on the study and will have an opportunity to ask questions and sufficient time to make up his/her mind concerning participation in the study. A signed and dated written IC will be obtained. All study-related assessments will be performed after the ICF has been signed.

At the first screening visit, subjects who have signed the ICF will receive screening numbers starting from 1-1001, and after assessment of inclusion and exclusion criteria, enrolled subjects will receive randomization numbers from the stratum specific list. During the screening/run-in period, the subjects will be interviewed for their relevant medical and surgical history and their prior and current use of medications. Demographic data will be also collected. This information may also be obtained from the subject's medical records, if available. If medical charts are used, relevant medical history events and concomitant medications should be verified with the subject (in order to ensure the subject does not use any medication not in his/her medical records). BP will be measured and safety laboratory tests will be performed at the first screening visit. If the investigator considers the subject to be eligible for the study based on these initial investigations, the subject may continue in the screening/run-in period.

During the screening/run-in period, the subjects will receive valsartan treatment that will replace their previous ACEI or ARB HF therapy. Valsartan during the screening/run-in period may be dispensed by any member of the study team. The screening/run-in dose of valsartan (80 mg BID or 160 mg BID) will be decided by the investigator based on the subject's clinical status, prior HF therapy and concomitant medications. The subjects will have a scheduled safety and efficacy assessment visit during the screening/run-in period (screening visit 2 in the study schedule, Table 3). If deemed sufficient by the investigator, screening visit 2 can be performed remotely. If so, safety blood sampling, eligibility criteria review, adverse events and concomitant medication must be assessed.

Dose reduction of a loop diuretic is allowed during the screening/run-in to prevent hypotension. Unscheduled visits may be performed at any time during the screening/run-in period. Study visit should be performed as close proximity to the stated day in the study schedule (Table 3) as possible.

The subject has to tolerate at the minimum 80 mg BID valsartan at a stable dose for minimum of 4 weeks in order to be eligible for the treatment period. Before the PET-scan, a urine pregnancy test should be performed for female subjects of childbearing potential. During the baseline visit, PET-scan and echocardiography will be done and blood samples for biomarker assessment will be drawn. After all other study procedures are performed at the baseline visit and the subject is deemed eligible for the study, he/she will be randomized and start the double-blinded treatment period.

The results for the laboratory tests taken during the on-site screening visits do not need to be available before decision-making (i.e. starting valsartan treatment), but they have to be reviewed as soon as possible after they become available in order to ensure subject safety. All screening/run-in period laboratory results must be available and reviewed before randomization, except the results of the laboratory tests taken on the baseline visit, as randomization is performed on the same day as the baseline visit.

Adverse events and changes in concomitant medications will be recorded throughout the screening/run-in period.

A subject will be entered into the study at the time of randomization, after the baseline PET-scan and echocardiography have been performed, if all inclusion criteria and none of the exclusion criteria are met.

For a detailed description on the information to be recorded during the screening/run-in period, please refer to Section 8.1.

### 7.2 Treatment period

The treatment period will last for approximately 8 weeks for each subject (it may be longer if required for clinical and/or scheduling purposes). During this time, the subjects will receive either sacubitril/valsartan or they will continue in the valsartan treatment arm. The subjects will be randomized into one of these two treatment arms in a 1:1 ratio. Study drugs during the treatment period will be dispensed by an unblinded member of the study team. As the different treatments, valsartan and sacubitril/valsartan, and the different strengths of these treatments are not similar in appearance, the study will be performed in a double-dummy manner, i.e. the subjects will take two tablets BID throughout the treatment period. The following options are possible:

- valsartan + placebo for sacubitril/valsartan,
- sacubitril/valsartan + placebo for valsartan.

The starting dose in the sacubitril/valsartan treatment arm will be 100 mg BID and in the valsartan treatment arm it will be 80 mg BID or 160 mg BID. A schematic figure about the possible treatments and doses is shown in Figures 2 and 3, Section 6.1. During the treatment period, the dose of the study treatment will be up-titrated to the

highest tolerated dose, up to 160 mg BID (if needed) for valsartan and up to 200 mg BID for sacubitril/valsartan. There will be one visit scheduled for possible up-titration of the dose (visit 1) and during this visit every subject should be attempted to be uptitrated to the next dose level (sacubitril/valsartan 200 mg or valsartan 160 mg, if needed), if clinically possible. If up-titration is not clinically possible, the starting dose should be maintained. At the minimum, 80 mg BID of valsartan or 100 mg BID of sacubitril/valsartan has to be tolerated by the subject in order to finish the study - if these doses are not tolerated, the subject has to be withdrawn from the study. The decision to up-titrate the dose will be done by the investigator during the study visits based on the subject's clinical status and the safety assessments, incl. BP and safety laboratory tests. The laboratory results, if taken on the days of the on-site visits, do not need to be available before decision-making but they have to be reviewed as soon as possible to ensure subject safety. If the safety blood samples are collected 1-2 business day(s) before the scheduled visit, the laboratory results have to be available and reviewed before decision-making. Dose reduction of a loop diuretic is allowed during the up-titration to prevent hypotension.

The day the subject starts taking the double-blind study medication is Day 1 (i.e. day of randomization) and the subsequent visits will take place on Day 14 (visit 1) and Day 21 (visit 2). Study visits should be performed as close proximity to the stated day in the study schedule (Table 3) as possible. Ideally, the last dose modification is done on visit 1. Visit 2 is a safety visit to be performed only for subjects for whom the treatment dose was modified on visit 1 and/or if it is clinically indicated based on the investigator's decision. If deemed sufficient by the investigator, visit 2 can be performed remotely. If so, safety blood sampling, adverse events and concomitant medication must be assessed. For subjects whose dose is not up-titrated on visit 1, visit 2 may be omitted, based on investigator's decision that has to be documented. Unscheduled visits may be performed at any time during the treatment period. Dose modifications, including up- and possible down-titrations are permitted during the first 4 weeks of the treatment period. Every effort should be made that the highest tolerated dose is reached on visit 1, at the latest, and only down-titrations are done after that, if clinically indicated. If dose is modified (down- and/or up-titrated) within the first 4 weeks, an unscheduled visit should be performed to assess subject safety on the new dose level. As dose modifications may be performed at any visit, the subjects will be asked to return their study medication at each site visit. They will be given new study drug packages or the same study drug packages will be returned to them, as applicable, according to the investigator's decision on dose modification.

The subjects will have to be on a stable dose of study treatment for a minimum of 6 weeks before visit 3. Visit 3 will include safety assessments (BP and safety laboratory tests), blood samples will be obtained for biomarker analysis and PET-scan and echocardiography will be performed. Before the PET-scan, a urine pregnancy test should be performed for female subjects of childbearing potential. The study ends for a subject after the last assessment is performed during visit 3; there will be no separate end-of-study visit. The subject will return the study medication to the site and he/she will continue his/her normal HF therapy, as advised by the investigator.

Adverse events and changes in concomitant medications will be recorded throughout the treatment period. Any possible serious adverse events (SAEs) or other clinically significant AEs, as judged by the investigator, will be followed up after the last study visit until resolution or until the event is considered chronic and/or stable.

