### Assessments:

Efficacy assessments: C-acetate PET scan, echocardiography and biomarkers

In order to assess cardiac efficiency and hemodynamics, PET imaging and echocardiography will be performed before randomization (after a minimum of 4 weeks on stable dose of 80 mg BID or 160 mg BID of valsartan) and repeated after 6 weeks on a stable dose of either 80 mg BID or 160 mg BID of valsartan or 100 mg BID or 200 mg BID of sacubitril/valsartan.

 $\frac{{}^{11}\text{C-acetate PET:}}{{}^{11}\text{C-acetate PET:}} Myocardial resting perfusion and oxygen consumption will be evaluated by {}^{11}\text{C-acetate PET}$  as tracer uptake (k1) and a mono-exponential clearance rate of {}^{11}\text{C-acetate (k\_{mono})}. Efficiency of left ventricle (LV) mechanical work will be calculated as follows: Efficiency = (LV work/gram of tissue) / oxygen consumption.

Echocardiography: Comprehensive echocardiographic evaluation of cardiac structure, systolic and diastolic function will be performed using 2D and 3D imaging, strain imaging and Doppler. LV mechanical work will be calculated as follows: LV work/gram of tissue= (SBP x SV x HR) / LV mass; where SBP is systolic blood pressure, SV is stroke volume and HR is heart rate.

Biomarkers: Biomarkers (N-terminal prohormone brain natriuretic peptide [NT-proBNP], hs-troponin and creatinine) will be measured to understand the possible mechanisms of the potential changes in myocardial efficiency.

Safety: Seated BP and HR will be measured at all site visits for safety assessment. BP and HR will be monitored also during the imaging sessions. All subjects will undergo blood laboratory tests, including serum potassium and creatinine, during the screening/run-in period on screening visits 1 and 2. The same laboratory assessments will be performed during the treatment period on visits 1-3, and also on unscheduled visits, if clinically indicated. If necessary to assess subject safety, more laboratory tests may be performed at any visit.

The decision to modify (up- or down-titrate) the dose level of a subject's study drug (either valsartan or sacubitril/valsartan) during the study may be done without the knowledge of the laboratory results; however, the results must be available and reviewed as soon as possible to ensure subject safety. Adverse events (AEs) and changes in concomitant medication(s) will be reported and documented throughout the study.

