The recommended starting dose of sacubitril/valsartan is one tablet of 49 mg/51 mg BID. The dose should be doubled at 2-4 weeks to the target dose of one tablet of 97 mg/103 mg BID, as tolerated by the patient. According to current recommendations found in the Summary of Product Characteristics (SPC) of sacubitril/valsartan, if patients experience tolerability issues (systolic blood pressure [BP[ ≤95 mmHg, symptomatic hypotension, hyperkalemia, renal dysfunction), adjustment of concomitant medications or temporary down–titration or discontinuation of sacubitril/valsartan is recommended. No dose adjustment is required in patients with mild renal impairment (estimated GFR [eGFR] 60-90 ml/min/1.73 m^2) while a starting dose of 24 mg/26 mg twice daily is recommended in patients with moderate renal impairment (eGFR 30-60 ml/min/1.73 m^2).

According to the information given in the EPAR – product information (annex 1) on the pharmacokinetics of sacubitril/valsartan, following oral administration, sacubitril/valsartan dissociates into valsartan and the prodrug sacubitril. Sacubitril is further metabolized to the active metabolite LBQ657 by carboxylesterases 1b and 1c. Sacubitril and LBQ657 reach peak plasma concentrations in 1 hour and 2 hours, respectively. They are highly bound to plasma proteins (94-97%). LBQ657 is not further metabolized to a significant extent. Approximately 50-70% of sacubitril (primarily as LBQ657) is excreted in urine and 30-50% in feces. Sacubitril, LBQ657 and valsartan are eliminated from plasma with a mean elimination half-life of approximately 1.4 hours, 11.5 hours, and 9.9 hours, respectively. The pharmacokinetics of sacubitril, LBQ657 and valsartan are approximately linear over

a sacubitril/valsartan dose range of 24 mg sacubitril/26 mg valsartan to 97 mg sacubitril/103 mg valsartan. The valsartan contained within sacubitril/valsartan is more bioavailable than the valsartan in other marketed tablet formulations; 26 mg, 51 mg, and 103 mg of valsartan in sacubitril/valsartan are equivalent to 40 mg, 80 mg and 160 mg of valsartan, respectively. (Gu 2010, Hubers 2016).

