# 4 STUDY DESIGN

# 4.1 Type and design of the study

This is a phase IV, prospective, randomized, double-blind, double-dummy, parallelgroup study performed at a single center that is formed by

. The subjects enrolled into this study will be patients with chronic HF who fulfill all of the inclusion criteria and none of the exclusion criteria. No more than 50% of the study subjects are allowed to have diabetes. The study will have two treatment arms, the sacubitril/valsartan treatment arm and the valsartan treatment arm, and the subjects will be randomized into these arms in a 1:1 ratio. The study will be performed in a double-blind manner in regards to the treatment the subjects receive during the treatment period. As the sacubitril/valsartan and valsartan tablets are not similar in appearance, the study will be performed in a double-dummy manner in order to maintain blinding, i.e. the subjects will take 2 tablets BID, either active valsartan + placebo for sacubitril/valsartan or active sacubitril/valsartan + placebo for valsartan. Regardless of the treatment arm a subject is in, the study drug will be up-titrated to the highest tolerated dose level during the scheduled study visits. The different strengths of the two study drugs are not identical in appearance so the possible dose modification(s) during the treatment period cannot be performed in a blinded manner. Subjects will start on valsartan 80 mg BID or sacubitril/valsartan 100 mg BID dose and there will be only one scheduled up-titration visit after the randomization. Exception for this are the subjects that are on valsartan 160 mg BID dose during the run-in phase. These subjects will be randomized directly to valsartan 160 mg BID or sacubitril/valsartan 100 mg BID. Subjects that are randomized to valsartan arm will have similar visit after which they will continue on the same dose. For subjects that were randomized from valsartan 160 mg BID to sacubitril/valsartan 100 mg BID the dose will be up-titrated to 200 mg BID if clinically possible. If clinically indicated, dose alterations will be allowed up to week 4 after randomization. In order to be eligible for the final study assessments on visit 3 (i.e. the C-acetate PET-scan and echocardiography), the subjects have to be on a stable dose for at least 6 weeks on one of the following treatment options: valsartan 80 mg BID or 160 mg BID or sacubitril/valsartan 100 mg BID or 200 mg BID. Study drug dispensing during the treatment period will be performed by an unblinded member of the study team and the study drugs will be self-administered by the subjects at home. To achieve similar groups, the number of subjects with renal insufficiency (GFR 45-60 or >60 mL/min/1.73m^2) and/or diabetes mellitus (on insulin or oral glucose-lowering therapy) will be balanced in the treatment arms by stratified randomisation. The baseline HF therapy (the number of subjects that are on valsartan 160 mg BID at the time of randomization) will be also balanced between the treatment arms.

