After the screening evaluations and confirmation of eligibility, the subjects will be allocated randomization numbers and randomized to receive the treatment assigned to each number in a blinded manner. Study drugs will be dispensed by an unblinded member of the study team member during the treatment period while the study personnel directly involved in the clinical assessments will remain blinded throughout the study. The starting dose for each subject in the sacubitril/valsartan arm will be 100 mg BID and in the valsartan arm 80 mg BID or 160 mg BID (see Figures 2 and 3). The study subjects will return to the study center 2-3 times during the treatment period at the following time points: approximately 2 weeks (visit 1), 3 weeks (visit 2) and 8 weeks (visit 3) after the start of the treatment period.

During visit 1, treatment tolerability will be evaluated and possible dose up-titration will be considered. Every subject should be attempted to be up-titrated to the next dose level (sacubitril/valsartan 200 mg or valsartan 160 mg, if the latter needed), if clinically possible. If up-titration is not possible, the starting dose should be maintained. The intent of visit 2 (week 3) is to confirm subject safety on the dose level that is likely to be maintained for the rest of the study. If deemed sufficient by the investigator, visit 2 can be performed remotely. If so, safety blood sampling, adverse events and concomitant medication must be assessed.

After visit 2, if clinically indicated, the dose of the study treatment may be modified (up- or down-titrated) up to week 4. If study drug dose is modified within this time, an unscheduled visit should be performed to assess subject safety on the new dose level. During the treatment period, the subjects will self-administer two tablets from two study drug packages BID (one tablet from the study drug package containing the active treatment and one tablet from the study drug package containing the placebo). The last study visit will include the final efficacy assessments, i.e. the C-acetate PET-scan and the echocardiography.

The general study design is presented in Figure 1 and the study outline is presented in Table 3. The methods and timing of assessments and recording of efficacy, safety, tolerability and other measures are described in detail in Section 8.

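### The day-14 dose doubling may go ahead before the first potassium and creatinine on randomised drug are read, which matters most in the GFR 45-60 stratum

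*Protocol*

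**What the plan says.** **Starting dose.** In its summary of product information, protocol section 2.3 states that "a starting dose of 24 mg/26 mg twice daily is recommended in patients with moderate renal impairment", with an eGFR range of 30-60. The trial recruits part of that range: subjects below 45 are excluded (section 5.4), and GFR 45-60 is a randomisation stratum (sections 4.1 and 4.2). Section 4.3 makes no renal adjustment: "The starting dose for each subject in the sacubitril/valsartan arm will be 100 mg BID", which section 6.1 defines as 49 mg sacubitril with 51 mg valsartan. The synopsis lists only the 49/51 mg and 97/103 mg strengths for use after randomisation. No reason is given for starting the GFR 45-60 stratum at the higher strength.

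**Up-titration.** Section 2.3 describes doubling after 2-4 weeks to a "target dose of one tablet of 97 mg/103 mg BID, as tolerated by the patient", and counts hyperkalemia and renal dysfunction among the tolerability issues. Sections 4.3 and 7.2 call for an attempt in every subject at visit 1, day 14, if clinically possible.

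**Laboratory results.** Section 7.2 says that the investigator decides "based on the subject's clinical status and the safety assessments, incl. BP and safety laboratory tests". It then adds: "The laboratory results, if taken on the days of the on-site visits, do not need to be available before decision-making". Results must still be reviewed as soon as possible. If blood was drawn 1-2 business days ahead, "the laboratory results have to be available and reviewed before decision-making"; that earlier draw is optional (Table 3, section 8.3.3). The synopsis, under Assessments, is broader: dose changes "during the study may be done without the knowledge of the laboratory results", with no restriction to same-day samples.

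**The concern.** Section 2.6 names hypotension, hyperkalemia and renal impairment as the reactions most often reported with sacubitril/valsartan. Blood pressure and symptoms can show the first at the visit. The other two are found by laboratory test. If same-day blood is drawn at visit 1, the doubling rests on clinical status, blood pressure and results obtained before sacubitril was given.

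The permission covers every subject in both arms. It carries most weight in the GFR 45-60 stratum, the one group for which the protocol itself quotes a lower start. A subject there whose potassium or creatinine has risen by day 14 could leave the visit with the doubled dose, and the rise would be seen only afterwards. What is at stake is the safety of individual subjects during conduct of the trial, not the validity of the efficacy comparison.

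**Working it through.** The plan gives no figure on this point to reproduce. The check is a comparison of doses and of the order of events.

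**1. Dose ratios** (tablet contents from sections 2.3 and 6.1)
- Start, sacubitril: 49/24 = 2.04 times the quoted start for eGFR 30-60.
- Start, valsartan component: 51/26 = 1.96 times.
- Visit 1 step, sacubitril: 97/49 = 1.98, a doubling.

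**2. Valsartan component by run-in dose** (section 2.3: 51 mg in the combination equals 80 mg of valsartan, and 103 mg equals 160 mg)
- From the 80 mg run-in: 80, then 80, then 160 mg equivalent. The last step is 160/80 = 2.0 and reaches a level that the run-in did not test.
- From the 160 mg run-in: 160, then 80, then 160 mg equivalent. The visit 1 step only restores a valsartan level already tolerated for at least 4 weeks.
- In both cases the sacubitril component is new at randomisation and doubles at visit 1.

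**3. Results that must be read before the doubling**
- Run-in samples on valsartan: must be read before randomisation (section 7.1).
- Baseline sample: exempt from that rule, because randomisation is on the same day (section 7.1). It is drawn before randomised drug in any case.
- Visit 1: the first scheduled sample on randomised drug (Table 3, section 8.3.3).
- Required on-drug results read before the doubling: 0 with same-day sampling, 1 with sampling 1-2 business days earlier.

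**4. When each safeguard acts**
- Before randomised drug: the section 5.4 exclusions (eGFR below 45, potassium above 5.2 mmol/l and creatinine above 1.5 x ULN, each if persistent; clinically significant renal disease as judged by the investigator) and at least 4 weeks on a tolerated valsartan dose.
- At visit 1 without a laboratory result: clinical status, blood pressure, and the section 5.8 withdrawal criterion for persistent symptomatic hypotension.
- Only once a result is read: the potassium and creatinine withdrawal criteria in section 5.8, and the rule for a confirmed creatinine rise of at least 25% in section 8.3.4.3.
- After the doubled dose is dispensed: review of the same-day sample as soon as possible, laboratory tests at visit 2 (day 21), and the unscheduled visit that section 7.2 asks for when the dose is changed in the first 4 weeks.

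**5. Number concerned.** The documents do not give the share with GFR 45-60. At an assumed 10-50%: 0.10 x 30 = 3 to 0.50 x 30 = 15 subjects in the sacubitril/valsartan arm, and 6-30 of 60 in both arms.

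**The case against.** The permission is open and deliberate. It stands in the synopsis and in section 7.2, and section 7.1 handles screening samples in the same way. Amendment item 1.2, which clarified that blood may be drawn 1-2 business days ahead, describes the text as matching the site's normal procedures. The unread-result situation may therefore be uncommon in practice. Subjects with raised potassium or creatinine on valsartan are screened out, the quoted lower start covers a range whose lower half is not enrolled, and a bad result can be answered by down-titration once it is read. All of this stands, and it lowers both the likelihood and the duration of the exposure. What remains is that early sampling is optional and no rule treats the GFR 45-60 stratum differently.

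Some stronger readings are tempting, but the documents do not support them:
- *A week of unmonitored exposure.* Day 21 minus day 14 is 7 days, but that is the interval to the next scheduled sample. The day-14 sample itself must be reviewed as soon as possible, so the exposure is the laboratory turnaround, which the documents do not state.
- *The starting dose is wrong.* The ratio of 2.04 shows why this stratum deserves care. The lower dose is a product-information recommendation quoted as background, its basis is not available here, and the fix leaves the dose alone.
- *Section 7.2 contradicts itself.* Basing the decision on laboratory tests and then not waiting for them sits uneasily, but the section sets separate rules for same-day and earlier samples and can be followed as written.
- *An excess of hyperkalemia is to be expected.* Section 2.6 reports 11.6% on sacubitril/valsartan against 14.0% on enalapril.

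**Conclusion.** The point holds as a modest matter of safety conduct. With same-day sampling at visit 1, the protocol allows sacubitril to be doubled (1.98-fold) with no potassium or creatinine result on randomised drug having been read. It matters most for GFR 45-60 subjects in the sacubitril/valsartan arm, who start at about twice the sacubitril dose that section 2.3 quotes for their renal range: 3-15 of 30 if their share is 10-50%. The exposure lasts from taking the doubled dose until the day-14 result is read and acted on. It is expected to be short, but the documents allow no figure for it, nor for the rate of abnormal results at day 14. A reader might infer bias in the primary comparison; nothing in the documents supports that, and none is claimed.

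The conclusion rests on the protocol's permission, not on evidence of what the site did. If the site always draws blood ahead of visit 1, the concern does not arise in practice and the change would only write that practice down.

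**What to change.** In section 7.2, Table 3 and the synopsis, require for subjects with GFR 45-60, in both arms so that blinding is kept, that potassium and creatinine from visit 1 are reviewed before the first up-titrated dose is taken. Either route would do:
- draw the sample 1-2 business days before the visit, within the window section 7.2 already provides; or
- draw it at the visit and hold the new dose until the result has been read, with the subject staying on the current dose meanwhile.

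Dose, strengths, eligibility and the visit 2 rules stay as they are.

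**Cost.** One earlier blood-draw trip for 6-30 of 60 subjects (same assumed share), or a short delay in the dose step. Visit 3 is tied to 6 weeks on a stable dose, so a hold of d days moves its earliest date from day 14 + 42 = 56 to day 56 + d, which Table 3 permits. A protocol amendment is also needed. The extra trip runs somewhat against amendment 1, which aimed to reduce site visits; the hold avoids it.

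**Timing.** The change is useful only while subjects are still being titrated. The SAP is dated April 2022, before database lock, so that stage may have passed; the documents do not say. Two optional reporting items would remain: a stated reason for the 49/51 mg start in this stratum, and a table of potassium and creatinine by GFR stratum, arm and visit alongside SAP section 2.6.3, which plans them by visit and arm only. The finding does not depend on either.
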